9. Conflict of Interest

There are no conflicts of interest with this project.

PANDA Ancillary Project Protocol

Protocol

1. Project Title

Pain and Nutrition in Dementia and Alzheimer's (PANDA); ancillary to the UCOPE Study:
Understanding Cognition, Oxytocin, and Pain in Elders)

2. Investigator(s)

[name] (PI)
[name] (co-I)

3. Abstract

Growing evidence suggests the presence of dysregulated pain modulation in older adults, and affect which may heighten age-associated risk for chronic pain. Additionally, chronic pain and Alzheimer's Disease and related dementias (AD/ADRD) are highly prevalent and comorbid in older adults, and research suggests that they may have overlapping etiologies and pathologies. Chronic pain may a predictor for the development of AD, and almost half of AD patients report having pain. Thus, understanding of the shared mechanisms underlying both is critical in order to develop effective treatment and prevention modalities. Recently, epigenetics has been implicated in both disease states, with many modifications of the epigenome that may go on to result in immune system dysfunction, of which is a hallmark of both chronic pain and AD. While there are many environmental factors that can influence the epigenome, nutrition status has been shown to be one of the most common and modifiable factors therein. Thus, it may be efficacious to understand dietary interactions with the epigenome to target epigenetic regulation of the development and maintenance of chronic pain and AD. Therefore, the overall goal for this mentored career development proposal is to fill this knowledge gap and determine the influence of overall diet pattern as well as Vitamins A and D specifically on the epigenetic environment as it relates to chronic pain and AD/ADRD. This study will assess dietary differences and their associations with differences in epigenetic aging, pain, and cognition in individuals with and without chronic pain. This proposed career development plan extends from the PIs prior work in dietary and immune system modulation of pain, and will forge a path towards understanding and investigating side-effect free nutrigenomic targets that improve pain and AD/ADRD outcomes in older adults.

4. Background

[figure not shown]

Figure 1. Prevalence of chronic pain by age and chronic pain grade (N=2497); adapted from Parsons et al., *Fam Pract*, Volume 24, Issue 4, August 2007, Pages 308–316.

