in chronic immune system activation and inflammation and epigenetic regulation. The relationship between inflammation and diet is well-documented, and many elements of diet have been reported to activate immune cells and trigger an inflammatory response³⁵⁻³⁶. Excess amounts of dietary oils and fatty acids have been shown to participate in lipid oxidation, leading to reactive oxygen species (ROS) and subsequent inflammation³⁷. Omega-6 polyunsaturated fatty acids (PUFAs), such as linoleic and arachidonic acid, are precursors for inflammatory prostaglandins³⁸, and are consumed in much higher amounts in the typical American diet than anti-inflammatory omega-3 fatty acids³⁹. Excess carbohydrates increase the presence of Advanced Glycation End Products (AGEs) that bind to immune cells and stimulate a pro-inflammatory response⁴⁰. In addition to pro-inflammatory effects, a diet can have anti-inflammatory effects as well. A Mediterranean diet can reduce markers of inflammation in obese individuals⁴¹ and in patients with osteoarthritis⁴² and rheumatoid arthritis⁴³⁻⁴⁴. Interestingly, one study found that the patients on a Mediterranean diet showed significant reductions in inflammatory markers prior to weight loss, suggesting that the diet itself produced anti-inflammatory effects⁴⁵. Studies have shown that specific micronutrients, such as Vitamins A and D, may have the ability to control gene expression by interacting with the epigenome. Both Vitamins A and D have their own receptors (Vitamin D Receptor or VDR, and the Retinoid X Receptor or RXR) are expressed both on cells as well as DNA^{46, 47} (**Figure 3**). These receptors can act as transcription factors participating in DNA transcription or physically block transcription from occurring, depending on the scenario. Additionally, there is also evidence to support that both vitamins and their receptors may participate in DNA methylation mechanisms, furthering their potential ability to influence the epigenome and downstream protein expression⁴⁸, many genes of which function to regulate the immune system and inflammation⁴⁹⁻⁵². Evidence suggests that not only are many chronic pain and/or AD patients deficient in these vitamins, but have differential DNA methylation status on these immune/inflammation-related genes influenced by Vitamins A and D ([name] et al, 2022, in process)⁵³⁻⁵⁵; and the subsequent differentially expressed genes may contribute to pain and cognitive decline⁵⁶. Additionally, there is evidence that Vitamin A deficiency may be associated with dysfunctional microglia⁵⁷. Vitamin D deficiency is a risk factor for the development of AD and chronic pain, and low levels of this vitamin are related to increased cognitive decline^{58, 59}. Vitamin D has also been shown to mitigate neuroinflammation present in the brain⁶⁰. Both basic science and clinical models also show that diets low in these micronutrients are linked to increased pain severity and disability in chronic pain, as well as increased A β and tau proteins in serum and PET scans, as well as more severe cognitive deficits in AD⁵⁸. In addition to being more cost-effective than most pharmaceutical interventions, nutrition based-interventions carry an incredibly positive side-effect profile. *Finally, nutrition interventions are highly adaptable, and can be adjusted to accommodate cost, flavor profiles, as well as be inclusive to cultural and religious practices, making them it a suitable strategy for all regardless of background.*

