Dietary Inflammatory Index. The Dietary Inflammatory Index (DII) was developed to provide a quantitative means for assessing the role of diet in relation to health outcomes ranging from blood concentrations of inflammatory cytokines to chronic diseases. **For the K99 phase**, diet data has been previously collected in the form of a 24-hour food recall. To collect diet data, participants were asked to document food and beverages consumed, as well as supplements taken 24 hours prior to their visit. Assessments were conducted interview-style by a trained research assistant in order to probe deeper into the details of meals. Visual aids such as standard measuring cups, plates, and drink cups in various sizes etc. were provided to aid in accuracy. These data will then be entered into the Nutrition Data System for Research (NDSR) for nutrient analysis. Following quantification, nutrient values will be used to calculate DII score according to the instructions laid out by Hebert & Shivappa et al⁶⁵.

Vitamin A and D Analyses. In order to quantify serum Vitamin D levels, the Quantikine[®] Human Vitamin D BP immunoassay (R&D Systems) will be employed. To quantify Vitamin A levels, a Colormetric Human Vitamin A ELISA Kit (Novus Biologicals) will be used. Kit-specific protocols will be used during quantification.

Epigenetic Analyses. Details regarding the protocol for processing and analyzing epigenetic data published elsewhere^{66, 67}. In short, the raw data generated by Illumina EPIC array (.idat files) will undergo quality control and normalization prior to the calculation of DNAmGrimAge via an online calculator (dnamage.genetics.ucla.edu). The age-adjusted AgeAccelGrim variable will be calculated as the difference between chronological age and DNAmGrimAge and used throughout the analyses.

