Hypotheses and data-analytic strategy: Prior to the testing of proposed hypotheses, each variable will be carefully examined to identify missing values, statistical outliers, and violations of relevant assumptions (i.e., Durbin-Watson, Shapiro-Wilk). Sensitivity analyses would then be completed to examine differences in results between variables with missing data and those same variables with data imputation. A corrected threshold will be set to 0.05, two-tailed. Descriptive statistics will be computed and represented as percentages or means (standard deviations). Group differences (pain impact groups; Vitamin A and D clinical cutoff differences) among potential covariates of interest will be examined using a series of one-way analysis of variance tests (ANOVAs) with follow-up/post hoc Bonferroni corrections. All participants will be matched on race and sex due to their relationships with pain and cognitive outcomes. All statistical analyses employed in this study were performed using SPSS (IBM) version 28.0 (IBM; Armonk, NY). Specific to hypotheses 1a-d: Sequential hierarchical multiple regression models will be employed to investigate the extent to which the continuous DII variable is associated with (H1a) greater severity, duration, and frequency of experimental and clinical pain outcomes, (H1b) accelerated epigenetic aging, and (H1c) worse cognitive decline between individuals with and without pain. Analyses of Variance (ANOVAs) will be performed in order to examine differences in variables of interest between groups: high-impact chronic pain, low-impact pain, and pain free controls. Additionally, three separate sequential hierarchical regression models within each group will be used to examine the extent to which higher scores DII scores are associated with epigenetic aging and cognitive outcomes. Variables of interest (DII, epigenetic age, cognitive status) will be entered into *step 1* of the analysis, relevant clinical covariates (e.g., BMI, smoking) will be entered in *step 2* of the hierarchical regression models, and relevant demographic variables (i.e., age, race, sex, etc.) in *step 3* of the regression models. Finally, a modified Poisson-regression analysis will be performed to assess the relative risk of clinical cognitive impairment between pain impact groups.

7. Possible Discomforts and Risks

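### The kit PANDA names for serum vitamin D reads as a binding-protein assay, so the vitamin D values and cutoff groups would not reflect vitamin D status

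*Combined protocol and SAP*

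**What the plan says.** In the PANDA protocol, section 6 (Research Plan), the paragraph on vitamin A and D analyses opens with its purpose: "In order to quantify serum Vitamin D levels". For this it states that the Quantikine "Human Vitamin D BP immunoassay (R&D Systems) will be employed". The next sentence deals with vitamin A: "a Colormetric Human Vitamin A ELISA Kit (Novus Biologicals) will be used". The paragraph closes by saying that the protocols supplied with the kits will be followed.

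The paragraph on hypotheses and data-analytic strategy uses the result once. It lists "Vitamin A and D clinical cutoff differences", together with pain impact groups, as group differences to be examined among candidate covariates by one-way ANOVA with Bonferroni post hoc corrections. It gives no cutoff value and no units.

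The PANDA abstract (section 3) describes the overall goal of the career development proposal as being to "determine the influence of overall diet pattern as well as Vitamins A and D specifically on the epigenetic environment". The background (section 4) explains the interest: "Vitamin D deficiency is a risk factor for the development of AD and chronic pain".

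**The concern.** The stated analyte and the named tool do not match. On the ordinary reading, the kit returns the concentration of a carrier protein. A clinical cutoff for vitamin D is a threshold on the vitamin itself, so it cannot classify anyone from a carrier-protein concentration. If the laboratory runs the named kit and the result is filed as vitamin D, each value in that column carries the wrong label, and groups formed from it do not separate people by vitamin D status. The error lies in what is measured, not in how precisely, so more participants or replicate assays would not correct it. Because the plan states neither cutoff nor units, nothing in it would expose the mismatch before analysis.

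**Working it through.** No arithmetic on effect size or power applies. The documents give no vitamin D mean, SD, cutoff or unit, so there is no stated figure to reproduce. The check is a comparison of what the plan wants to measure, what it names for the purpose, and how it uses the result.

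1. **Intended quantity.** The purpose clause in the vitamin paragraph is serum vitamin D level. The background in section 4 agrees: it speaks of deficiency and low levels of the vitamin, and the receptor it describes is the vitamin D receptor. It does not discuss a carrier protein.

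2. **Named assay.** The kit is called Vitamin D BP. The documents do not expand BP. Binding protein is its ordinary meaning in an assay name. The vitamin A kit in the next sentence is named for the vitamin alone, with no such suffix, so the suffix on the vitamin D kit carries meaning.

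3. **Anything else that could supply a vitamin D level.**
   - The urine and blood paragraph lists a comprehensive metabolic panel, neuropeptides, inflammatory markers and genetic markers. None is a vitamin D measure.
   - The food recall yields nutrient values that go into the Dietary Inflammatory Index. These describe intake, and the plan does not offer them as a serum level.
   - No 25-hydroxyvitamin D or other metabolite assay appears in either protocol, and no step converts a BP result into a vitamin D level.

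4. **Use of the result.** The analysis paragraph forms groups by a clinical cutoff for vitamin D. That step needs the vitamin's own concentration.

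5. **Number affected.** From the Participants paragraph: 50 with previously collected data and stored blood + 40 newly enrolled = 90. This is an upper limit, since the total includes a 20% allowance for attrition.

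6. **Reach.** The only PANDA aim, in section 5, has hypotheses H1a-d on the Dietary Inflammatory Index, epigenetic aging, cognition and pain group. The regression steps name that index, epigenetic age and cognitive status, then clinical covariates (BMI and smoking as examples), then demographic variables. Vitamin D is named in none of them. The UCOPE analyses in its Table 3 do not use vitamin D either.

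**The case against.** The strongest reply has three parts.

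**It may be a naming slip.** The purpose clause is clear, BP is never spelled out, and what a commercial kit reports cannot be checked from the documents. The team may intend, and use, a true vitamin D assay. This is possible, and it is why the conclusion is conditional on the text being followed. It does not clear the text: the named kit and the stated analyte would still conflict, and the laboratory is told to follow the kit's own protocol.

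**The consequences are easily overstated.** A reader might infer that a main PANDA comparison of deficient with sufficient participants is invalid, or that the study's central goal fails. The documents do not support this. The full sentence about cutoffs places them in a descriptive look at candidate covariates, ahead of the hypothesis tests. Grouping as deficient or sufficient is not the plan's wording. The goal that names vitamins A and D belongs to the wider career development proposal. The abstract then describes this study as one of dietary differences, epigenetic aging, pain and cognition, and H1a-d contain no vitamin D hypothesis. This part of the objection stands, and it sets the weight of the point.

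**The remedy goes beyond the documents.** They do not mention 25-hydroxyvitamin D, and they give neither assay prices nor the volume remaining in the stored samples. This also stands in part. The metabolite is offered here as an example, and it is not shown that the 50 stored samples can support another assay.

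**Conclusion.** The point holds, at moderate weight. As written, the plan names an assay that on its ordinary reading measures a different analyte from the one it sets out to quantify. The vitamin D values, for up to 90 participants, and the vitamin D cutoff grouping would then not reflect vitamin D status.

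This rests on two assumptions: that BP means binding protein, and that the named kit is the one run. The effect is confined to the PANDA vitamin D measure, the covariate comparisons that use it, and the vitamin D part of the proposal's overall goal. The H1a-d models are unaffected as they are named. Their covariate list is given by example, so this would change only if the vitamin D value were later brought in as a covariate, which the plan does not say.

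It would be wrong to read this as a defect in the UCOPE trial. PANDA is an observational ancillary study, and UCOPE's randomised comparison and outcomes do not depend on this assay.

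**What to change.** Two paragraphs in PANDA section 6 need editing.

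- **Vitamin A and D analyses.** Replace the Vitamin D BP kit with an assay that measures circulating vitamin D, and name the analyte (for example 25-hydroxyvitamin D). Use the same blood, after confirming that enough volume remains in the 50 stored samples.
- **Hypotheses and data-analytic strategy.** State the vitamin D cutoff with its units, and apply it to that analyte only.

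If binding protein is really what is wanted, report it under its own name and do not apply a vitamin D cutoff to it. If the kit name is a transcription error, correct the name and still add the cutoff and units.

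The cost is a short text change and a change of kit before the assay is run, on blood that is already stored or planned for new participants. The documents give no kit price and no remaining sample volume, so the laboratory must confirm both. If some stored samples are too small, the number with a vitamin D value will fall below 90 and should be reported.

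### PANDA's epigenetic acceleration variable is labelled age-adjusted but defined as a plain difference from age, and the pain-impact group ANOVAs have no age term to make up for it

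*Combined protocol and SAP*

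**What the plan says.** All of this is in the PANDA Ancillary Project Protocol, section 6 (Research Plan).

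- **Definition (Epigenetic Analyses).** "The age-adjusted AgeAccelGrim variable will be calculated as the difference between chronological age and DNAmGrimAge and used throughout the analyses". No regression on age is described. The same paragraph refers the reader to outside sources: "Details regarding the protocol for processing and analyzing epigenetic data published elsewhere".
- **Group comparison (Hypotheses and data-analytic strategy).** "Analyses of Variance (ANOVAs) will be performed in order to examine differences in variables of interest between groups", the groups being high-impact pain, low-impact pain and pain-free controls. No covariate is named. Epigenetic age is listed among the variables of interest.
- **Matching.** "All participants will be matched on race and sex due to their relationships with pain and cognitive outcomes". Age is not a matching factor.
- **Covariate screening.** "Group differences (pain impact groups; Vitamin A and D clinical cutoff differences) among potential covariates of interest will be examined" by one-way ANOVA. No rule says what happens to the outcome ANOVAs if age turns out to differ.
- **Regressions.** Variables of interest enter at step 1 and clinical covariates at step 2. The plan puts "relevant demographic variables (i.e., age, race, sex, etc.) in" step 3.

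**The concern.** A variable described as age-adjusted invites the analyst and the reader to treat it as free of age, so that no further adjustment seems necessary. The plan acts on that view: its group ANOVAs carry no age term. If the subtraction does not remove age, a difference in mean age between pain-impact groups becomes a difference in apparent acceleration. The error can run either way. With b below 1 an older group looks as if it is ageing more slowly, which could create a spurious finding or hide a real one.

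An age imbalance is possible in this sample. PANDA pools 50 stored participants from the parent study, whose age floor for older adults is 45, with 40 new enrollees recruited under a floor of 55 for knee osteoarthritis. No age range is given for the pain-free controls.

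The direction of the difference is also left open. Taken in the order written (chronological age first), faster ageing would come out negative, whereas hypothesis H1b speaks of accelerated ageing.

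**Working it through.** The plan gives no figure on this point, so there is none to reproduce.

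**Inputs from the documents.** Total N is 90 (50 stored + 40 new). The 20% attrition allowance leaves 90 × 0.8 = 72. The threshold is 0.05, two-tailed. There are three groups.

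**Inputs assumed, because the documents do not give them.** Equal groups of 30 (24 after attrition); age SD 8 years within group; residual SD of DNAmGrimAge given age 4.5 years; slope b from 0.7 to 1.0; gap d in mean age between the extreme groups from 0 to 8 years, with the middle group halfway.

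**Step 1: what subtraction leaves.** Write DNAmGrimAge = a + b × age + e. Then DNAmGrimAge - age = a + (b - 1) × age + e. Its correlation with age is

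(b - 1) × 8 / √[((b - 1) × 8)² + 4.5²].

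For b = 0.7 this is -2.4 / √(5.76 + 20.25) = -0.47. For b = 0.8 it is -0.34 and for b = 0.9 it is -0.18. For b = 1 it is 0.

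**Step 2: effect on the group ANOVA.** With no true group effect, the group means differ only through age: the extreme groups lie (b - 1) × d apart. At b = 0.7 and d = 5 that is -1.5 years. The noncentrality parameter is

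λ = n × Σ[(b - 1) × group age deviation]² / [((b - 1) × 8)² + 4.5²].

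For b = 0.7, d = 5, n = 30, the deviations are -2.5, 0 and +2.5, so λ = 30 × 0.09 × 12.5 / 26.01 = 1.30. With a noncentral F on 2 and 87 degrees of freedom, the rejection rate at 0.05 is 15.6%. The other settings, at 30 per group:

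| Age gap d | b = 1.0 | b = 0.9 | b = 0.8 | b = 0.7 |
|---|---|---|---|---|
| 0 years | 5.0% | 5.0% | 5.0% | 5.0% |
| 2 years | 5.0% | 5.2% | 5.8% | 6.5% |
| 5 years | 5.0% | 6.3% | 10.1% | 15.6% |
| 8 years | 5.0% | 8.5% | 19% | 34% |

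With 24 per group, the 5-year row is 6.0%, 9.0% and 13.2% for b = 0.9, 0.8 and 0.7.

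**Step 3: effect on the regressions.** Once age is in the model, the raw difference, the residual and DNAmGrimAge itself differ only by a constant and a multiple of age, which the age term absorbs. The DII coefficient must then be the same for all three. In one simulated set of 90 (b = 0.75, residual SD 4, DII mildly related to age), the step 3 DII coefficient was -0.3254 (p = 0.469) for all three outcomes. Before age entered, it was -0.75 (p = 0.13) with the raw difference and -0.31 (p = 0.48) with the residual. Only steps 1 and 2 and the ANOVAs depend on the definition.

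**Step 4: does the fix work?** Simulated rejection rates with no true group effect, b = 0.7, 30 per group, residual SD 4, 4,000 runs per setting:

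| Age gap | Raw difference, ANOVA | Residual, ANOVA | Raw difference, ANCOVA with age |
|---|---|---|---|
| 4 years | 11.8% | 3.9% | 4.2% |
| 8 years | 40.2% | 4.0% | 5.0% |

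The residual ANOVA is slightly conservative because a pooled regression on age absorbs part of any group difference that lies along the age trend. That share is the between-group part of the age variance: (2 × 2.5² / 3) / (2 × 2.5² / 3 + 64) = 6% at a 5-year gap, and 14% at 8 years by the same formula.

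**The case against.** The strongest reply is that the harm needs two conditions, a slope other than 1 and unequal mean ages, and the documents establish neither. If either fails, the ANOVA error rate is 5%. That stands. A reader might infer that PANDA's group results will be confounded by age; the documents do not support so firm a statement. The different age floors make imbalance possible and do not show it.

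A reader might also infer that the test of H1b is invalid. It is not. H1b concerns the association of DII with accelerated ageing, it is tested by hierarchical regression, and the final step adjusts for age. The ANOVAs look at the variables of interest by group, and no separate hypothesis of a group difference in acceleration is stated.

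The definition is a one-sentence summary that points to outside methods, so the actual computation may be sound. That is possible but cannot be checked: the entries printed under the two cited numbers in the PANDA reference list concern intranasal oxytocin safety and pain rating scales. Nor is the sign shown to be wrong, since the difference between two quantities need not fix the order of subtraction; it is unspecified.

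Lastly, the covariate screening could reveal an age imbalance. This helps only in part, because no adjustment follows from it.

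**Conclusion.** The concern holds in a limited form. The label and the formula disagree, and that follows from algebra alone. Neither matching nor a covariate protects the group ANOVAs from age. How much this matters depends on quantities the plan does not state: from no effect (b = 1 or equal ages), through 5% to 7% false positives at a 2-year gap, to 34% at an 8-year gap with b = 0.7. These figures assume an age SD of 8, a residual SD of 4.5 and 30 per group, with b from 0.9 to 0.7 for the 2-year range. The step 3 DII coefficient is unaffected; steps 1 and 2 are affected if DII is related to age. PANDA is a cross-sectional observational study, so nothing here touches the randomised oxytocin comparison in UCOPE.

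**What to change.** 1. Define AgeAccelGrim as the residual from regressing DNAmGrimAge on chronological age across all PANDA participants, and state that positive values mean faster ageing.
2. Replace the pain-impact group ANOVAs with ANCOVA including age. Residualising one variable would leave the other ANOVA outcomes, DII and cognition, unadjusted. With age in the model, the group test also no longer depends on which epigenetic variable is used.
3. Reconcile the analysis section, which names epigenetic age as a variable of interest, with the definition paragraph, which says AgeAccelGrim is used throughout.

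The cost is one error degree of freedom (87 to 86 with 90 participants) and small changes to wording and code. No new data are needed.
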